# 9.3.2 Scenario 2:

One combination (G) has true DLT probability more toxic than 33% and the three combinations in Zone 2 have the highest IRR among safe combinations. The true range of optimal combinations is indicated in italicized bold type.

Table 18: Study Scenario 2

Zones		1			2		
Combination	Α	В	С	D	E	F	G
True DLT probabilities	5%	6%	8%	22%	23%	25%	45%
True IRR	45%	50%	50%	65%	65%	65%	80%
% optimal combination recommendation	6%	10%	10%	25%	22%	20%	5%
% participant allocation	12%	14%	13%	18%	18%	17%	8%
Average trial size: 45 participants (25th, 50th, 7	′5 th perc	entile =	39, 44,	52)			

2.2% of simulated trials were stopped for safety

The overall toxicity rate was 18.3%. The overall IRR was 60.0%.

#### 9.3.3 Scenario 3:

Combinations in Zones 2 and 3 have true DLT probabilities more toxic than 33% and the two combinations in Zone 1 have the highest IRR among safe combinations. The true range of optimal combinations is indicated in italicized bold type.

Table 19: Study Scenario 3

Zones		1			2		3
Combination	Α	В	С	D	Е	F	G
True DLT probabilities	18%	20%	25%	45%	48%	54%	64%
True IRR	65%	70%	70%	80%	80%	80%	90%
% optimal combination recommendation	19%	28%	25%	1%	1%	0%	0%
% participant allocation	25%	29%	29%	6%	6%	5%	1%

Average trial size: 29 participants (25th, 50th, 75th percentile = 21, 33, 39)

25.2% of simulated trials were stopped for safety

The overall toxicity rate was 25.4%. The overall IRR was 70.6%.

#### 9.3.4 Scenario 4:

All true DLT probabilities are unsafe (i.e. more toxic than 33%).

Table 20: Study Scenario 4

Zones		1			2		3
Combination	Α	В	С	D	Е	F	G
True DLT probabilities	50%	55%	56%	65%	66%	74%	80%
True IRR	70%	70%	70%	80%	80%	80%	90%
% optimal combination recommendation	1%	1%	3%	0%	0%	0%	0%
% participant allocation	32%	28%	35%	2%	2%	1%	0%

Average trial size: 7 participants (25th, 50th, 75th percentile = 2, 3, 6)

96% of simulated trials were stopped for safety

The overall toxicity rate was 45.6%. The overall IRR was 70.3%.

## 9.4 Study design Part 2

A fixed sample size design will be used in part 2. The vaccine regimen is selected based on available data from Part 1, in which the recommended combination was Arm E. For Part 2, all accruals will be to Study Arm E2.

#### 9.5 Sample size/accrual

#### 9.5.1 Part 1 (completed)

Maximum sample size is based upon acquiring sufficient information to assess the objective of selecting the arm with the highest IRR, assuming at least one optimal combination has been found.

Data from our prior Mel43 trial in the arms not getting GM-CSF  indicated a high T cell response (5-fold increase in reactivity, at least 1200 cells per 100,000 CD8, and no overlap

Version Date: 07-31-17

of 2 SD) to the 12 peptide vaccine in PBMC in 30 of 60 participants (50%, 95%Cl (37%, 63%)). Using the range as an approximate guideline, maximum sample size is established to ensure that if IRR among all seven arms differ by 30%, with the smallest expected rate of 50%, then the arm with the higher IRR would be selected with high probability, P=0.90. The initial maximum target accrual of 20 eligible participants per arm is based upon the ranking and selection procedure,  $B_{SH}$  75, which allows selection of the best treatment worthy of further investigation in single-factor Bernoulli response experiments. However, it is not anticipated that all arms will fall in the range of optimal combinations, thus, sample size is estimated from the simulations and will be determined by the stopping rules below. Although maximum accrual is set at 140, in the simulation results below, on average a total of between 7 and 46 participants were required to complete the study.

Accrual is estimated at 2 participants per month at each site (4 per month overall). The maximum accrual to the study is estimated from the simulations to be approximately 52 participants. Adjusting for 10% ineligibility/dropout/withdrawal rate, maximum total target accrual for Part 1 is estimated at 58 participants.

## 9.5.2 Part 2

Immune response was observed in 6/16 (37.5%, 90%Cl [17.8, 60.9%]) from Part 1. For Part 2 target accrual is set at 16 eligible participants. At study conclusion, if we observe that at least 12/16 (a doubling of the response rate) eligible participants satisfy the definition of immune response then the lower limit of a one-sided 80%Cl around the observed immune response rate for Arm E2 would be 61.5% which we would conclude supports that the immune response rate is likely to be higher for single site injections. If fewer responses are observed then additional studies will be needed to better understand the impact of site rotation with the use of the tetanus helper peptide.

Accrual is estimated at 2 participants per month. Adjusting for 10% dropout rate, maximum total target accrual for Part 2 is estimated at 18 participants.

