#### 9.2.3 Combination recommendation:

Once the set of "acceptable" combinations is determined, the recommended combination will be based upon how many participants have been entered into the study to that point. If less than 3 participants have been treated on any acceptable dose, then the recommended combination for the next entered participant will be chosen at random from the acceptable combinations. If at least 3 participants have been treated at every acceptable combination, the recommended combination for the next participant entered is defined as the "acceptable" combination with the highest observed IRR. After each participant, a new recommended combination is obtained, and the next entered participant is allocated to the recommended combination. Part 1 of the trial will stop once sufficient information about the optimal dose range has been obtained, according to the stopping rules outlined in Section 9.6.1.

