## 9.6 Stopping rules:

## 9.6.1 Part 1 (completed)

The study will be stopped according to the following rules:

- 1. The study will stop early for safety if the first three entered participants in Zone 1 experience DLT on combinations in Zone 1 in Stage 1.
- 2. If at any point in Stage 2, the set of acceptable combinations is empty, the trial will stop for safety.
- 3. The study will stop if the recommendation is to assign the next participant to a combination that already has 20 participants treated at that combination.

#### 9.6.2 Part 2

Safety will be assessed by monitoring the number of participants who experience a DLT. In Part 1, 1/16 (6.3%, 95%Cl [0.2, 30.2%]) participants treated on Arm E experienced a DLT. For Part 2 the upper boundary of a sequential probability ratio test (SPRT) based upon a binomial test of proportions for DLT will be used for monitoring to protect against excessive DLT rates. The stopping boundary is for a SPRT contrasting a 5% versus 30% DLT rate, with nominal type I and II errors of 5% and 20%, respectively. Safety stopping guidelines for the occurrence of DLTs are detailed in the following table. If a stopping bound is crossed then accrual to the study will be suspended until the study PI, co-investigators and the DSMC can review the data, and determine if the study should continue, be amended or be closed to further accrual.

Version Date: 07-31-17

Table 21: Incidence of Treatment-Related DLTs

Incidence of treatment related DLTs					
Number of participants   Stopping boundary					
2-4	≥2				
5-11	≥3				
12-18	≥ 4				

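### The 0.90 probability of selecting the best arm in Section 9.5.1 holds for a fixed 20 participants in each of seven arms, not for the adaptive rules that Part 1 used

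*Combined protocol and SAP*

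**What the plan says.** Section 9.5.1 sets the configuration for the sample size: "if IRR among all seven arms differ by 30%, with the smallest expected rate of 50" percent. In that case, it says, "then the arm with the higher IRR would be selected with high probability, P=0.90". The basis follows: "The initial maximum target accrual of 20 eligible participants per arm is based upon the ranking and selection procedure" for Bernoulli responses. Seven arms of 20 make 140.

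The same section then moves away from that size. It does not expect every arm to fall in the optimal range, "thus, sample size is estimated from the simulations and will be determined by the stopping rules below". It adds: "Although maximum accrual is set at 140, in the simulation results below, on average a total of between 7 and 46 participants were required". Finally: "The maximum accrual to the study is estimated from the simulations to be approximately 52 participants", or 58 after a 10% allowance for losses.

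The operating rules are elsewhere. Section 9.2.3 assigns at random among acceptable combinations while any of them has fewer than three participants. "If at least 3 participants have been treated at every acceptable combination", the next participant goes to the one with the highest observed immune response rate (IRR). Section 9.2.1 (Zone 3) has the same switch when no DLT has occurred. Section 9.6.1, rule 3, ends accrual: "The study will stop if the recommendation is to assign the next participant to a combination that already has 20 participants treated" there.

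**The concern.** The only selection probability that the sample-size section states comes from a design that was not going to be run: seven arms of 20 cannot fit into about 52 participants. After the first three per arm, allocation follows the observed leader. A best arm with a poor start can then be left behind, and the trial stops once another arm reaches 20.

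The four scenarios in Section 9.3 do not fill the gap, because none has one arm at 80% and six at 50%. The nearest is Scenario 1 (best 80%, next 65%, others lower), where the best arm is recommended in 62% of trials. A reader who wants the chance of a correct selection under the sizing assumption finds only 0.90, and that does not describe the design used.

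**Working it through.** **Inputs from the plan.** Seven arms, one with IRR 0.80 and six with 0.50; 20 per arm; stated probability 0.90 (Section 9.5.1). Three per acceptable arm, then highest observed IRR (9.2.1, 9.2.3). Stop when the recommended arm has 20 (9.6.1). DLT limit 33%, with six orderings and the working models (9.2.2, Tables 15 and 16). Scenario 1 DLT rates 1, 2, 5, 7, 11, 14 and 20% for A to G (Table 17).

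**Assumptions that the plan does not give.** DLT rates for the 0.80 v 0.50 case, the delay before an immune result is known, random breaking of ties, and the reading of the random phase. That phase may draw only from arms with fewer than three participants (reading 1) or from all acceptable arms until each has three (reading 2).

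**Step 1: reproduce 0.90.** Let f and F be the binomial(n, 0.50) probability and cumulative probability. With random tie-breaking,

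P(correct) = Σₓ Pr[Bin(n, 0.80) = x] × Σⱼ C(6, j) f(x)ʲ F(x−1)⁶⁻ʲ / (j+1), for j = 0 to 6.

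- n = 19: 0.898
- n = 20: 0.908

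So 20 is the smallest number per arm that reaches 0.90, and the plan's figure is reproduced for 7 × 20 = 140.

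**Step 2: actual rules, no DLTs.** The run-in, the random phase, the switch to the leading arm and the stop at 20 were simulated with 1,200 trials for each of the seven positions of the best arm. The Monte Carlo standard error of an average over positions is about √(0.75 × 0.25 / 8,400) = 0.005.

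| Random phase | Immune result known | P(correct) | Mean size |
|---|---|---|---|
| Reading 1 | at once | 0.75 | 44 |
| Reading 1 | after 4 more participants | 0.76 | 47 |
| Reading 2 | at once | 0.79 (about 0.81 if G is best) | 55 |
| Reading 2 | after 4 more participants | 0.78 | 58 |

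When the trial stops, one arm has 20. The other six average (44 − 20)/6 = 4.0 under reading 1 and (55 − 20)/6 = 5.8 under reading 2.

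**Step 3: add DLTs.** The continual reassessment model of Section 9.2.2 was fitted by maximum likelihood, with 700 trials per position of the best arm. Each range covers both readings and both delays.

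| DLT rates | P(correct), averaged over position of the best arm |
|---|---|
| Half of Scenario 1 | 0.74 to 0.78 |
| Scenario 1 | 0.72 to 0.75 |
| 5% in every arm | 0.70 to 0.73 |
| Scenario 1, G best (no averaging) | 0.62 to 0.66 |

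**Step 4: check the simulation against the plan.** For Scenario 1, reading 1 gives mean size 43, quartiles 39, 42 and 47, and G selected in 57% of trials. Table 17 gives 45, then 40, 43 and 48, and 62%. The simulation stops for safety in about 3% of trials against 0.4% in the plan, so the figures with DLTs may be 2 to 5 points too low. The no-DLT figures are not affected.

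**The case against.** The best reply is that Section 9.5.1 does not promise 0.90 for the adaptive trial. It ties the figure to a maximum, calls 20 per arm an initial target, and says at once that simulations and stopping rules will set the size. Section 9.3 reports how often each arm is recommended under the actual rules, and the 62% in Scenario 1 is hardly flattering. Adaptive allocation is also efficient: an equal split of 52 gives seven or eight per arm, for which the formula in Step 1 returns only 0.62 to 0.66.

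Much of this stands. The plan shows where 0.90 comes from, and the adaptive rules are not a poor choice. But the reason given for leaving 140 is that not every arm will be in the optimal range. The shortfall in Step 2 arises with all seven arms acceptable throughout. The 0.90 is neither withdrawn nor restated, and Section 9.3 uses other response rates.

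Four stronger readings are tempting, and the documents do not support them:

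- **That 0.90 is an arithmetic error.** It is right for the fixed design.
- **That the plan's own assumptions imply a 20 to 25% chance of a wrong choice.** Absence of DLTs and immediate results are assumptions made here; every scenario in Section 9.3 has DLTs.
- **That the choice of Arm E for Part 2 rests on the 0.90.** Section 9.0 gives other grounds: the strongest responses were in E and G, resiquimod was no longer available, and E had the larger enrolment.
- **That Arm E should not be called optimal.** Section 9.1 defines the term by estimated toxicity and response, so a change of word would be a preference.

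**Conclusion.** The concern holds as a mismatch between a stated property and the design used. For the sizing configuration, the adaptive rules give about 0.75 to 0.81 without DLTs, 9 to 15 points below 0.90; wrong selection is then 19 to 25% rather than 10%. The delay before immune results hardly matters in these runs, while the reading of the random phase moves the result by 2 to 4 points on average.

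The no-DLT range should be taken as an upper one. Low to moderate DLT rates bring the average to about 0.70 to 0.78, and a best arm that is also the most toxic brings it to 0.62 to 0.66 at Scenario 1 rates. The figures with DLTs depend on assumed rates and carry the 2-to-5-point caution from Step 4. Part 1 is complete, so the finding bears on how its selection is described, not on its conduct.

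**What to change.** In Section 9.5.1, state that 0.90 applies to a fixed 20 participants in each of seven arms (140 in total). Beside it, report the simulated probability of selecting the best arm under Sections 9.2 and 9.6.1 for 0.80 v 0.50, and state the assumed DLT rates, the delay before immune results and the reading of the random phase. The sponsor's own simulation program is the best source for that figure. A single unqualified number such as 0.75 to 0.80 would repeat the problem.

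The cost is one added simulation scenario and a few sentences. No allocation rule, stopping rule or Part 2 sample size changes. The stated probability becomes less favourable.

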# 9.0 STATISTICAL CONSIDERATIONS

This is an open-label, Phase I/II study evaluating the safety and immunogenicity of a long peptide vaccine (LPV7) + TLR for resected stage IIB – IV melanoma. There are two parts to the study.

For Part 1, the trial was designed to find the range of optimal combination therapies, defined as combinations with high immunologic response and an acceptable level of toxicity. The primary outcomes included the frequency of treatment related dose limiting toxicities (DLTs) and frequency of immunologic response. For Part 2, the goal is to obtain preliminary safety and immunogenicity data on the optimal combination identified in Part 1 when administered in the same skin site for all 6 vaccines (same site vaccination).

For part 2, the vaccine regimen is selected based on available data from Part 1, in which the strongest immune responses were observed in participants enrolled on Arms E and G (Table 1A). Resiquimod is no longer available; so the regimen for Arm G is not currently feasible. Also, the total enrollment on Arm E is larger (15 vs 6) so that outcomes from Part 2 will be evaluable in a similar sample size as for Part 1, Arm E. This group will be called Study Arm E2.

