# 9.7.2 Immunologic response:

Subjects are evaluable for immune response if at least one post treatment sample is measurable for response. Peak immunogenicity will be evaluated by direct Elspot assay against the defined nonamer peptides in the peripheral blood. The presence or absence of an immune response will be defined by induction of at least a 2-fold increase in IFN-gamma-secreting cells over background, and over pre-existing responses, and at least 30 IFN-gamma secreting spots per 100,000 CD8 T cells, as described . This assessment will be performed on blood through week 12, although a minimum of 4 weeks of data will be used to guide decisions about the range of optimal dose combinations. IRR is defined as the proportion of participants where presence (as defined above) of an immune response has been observed.

Durable immunogenicity will be evaluated week 26 by Ellspot assay against the defined nonamer peptides in the peripheral blood. The presence or absence of an immune response at that time will be defined by induction of at least a 2-fold increase in IFN-gamma-secreting cells over background, and over pre-existing responses, and at least 30 IFN-gamma secreting spots per 100,000 CD8 T cells, as described . This assessment will be performed on blood through week 26.

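### Does the count of 15 for Arm E in section 9.0, against 16 in sections 9.5.2 and 9.6.2, undermine the Part 2 benchmark?

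*Combined protocol and SAP*

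**What the plan says.** Section 9.0 explains why Arm E rather than Arm G goes forward. One reason is that resiquimod is no longer available. Another is that "the total enrollment on Arm E is larger (15 vs 6"), so that Part 2 can be read against a Part 1 arm of about the same size.

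Section 9.4 repeats that the choice rests on Part 1, "in which the recommended combination was Arm E".

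Section 9.5.2 gives the benchmark as "Immune response was observed in 6/16 (37.5"%, with a 90% interval of 17.8 to 60.9%), without naming the arm. It continues: "For Part 2 target accrual is set at 16 eligible participants". The immunogenicity criterion is that "at least 12/16 (a doubling of the response rate) eligible participants satisfy the definition of immune response". In that case the one-sided 80% lower limit on the "immune response rate for Arm E2 would be 61.5"%.

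Section 9.6.2 states that 1/16 (6.3%, 95% interval 0.2 to 30.2%) "participants treated on Arm E experienced a DLT".

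Section 9.7.2 defines the analysis set for response: "Subjects are evaluable for immune response if at least one post treatment sample is measurable for response".

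**The concern.** Part 1 is marked as completed, so Arm E should have one enrolment count. Section 9.0 calls 15 the total; section 9.6.2 counts 16 as treated. The usual explanation, that one number is a subset of the other, runs the wrong way here: an evaluable or eligible set can be smaller than total enrolment, but a treated set cannot be larger. No section mentions a data cut-off, a replacement or an exclusion that would account for the extra participant.

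Part 2 is a single non-randomised arm, so its response rate can be read only against the Part 1 figure, and 6/16 is the stated origin of 12/16. If the denominator were really 15, the response rate, its interval and the description of 12/16 as a doubling would all be off. Section 9.5.2 also leaves three details implicit: the arm behind 6/16, whether 16 means treated, eligible or evaluable, and the value with which the 61.5% limit is compared.

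**Working it through.** **Inputs.** Arm E count: 15 (section 9.0) or 16 (section 9.6.2). Responders 6, denominator 16 (9.5.2). DLTs 1 (9.6.2). Criterion 12/16, one-sided 80% limit, dropout 10% (9.5.2). Sequential test: 5% versus 30%, type I error 5%, type II error 20% (9.6.2).

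**Step 1: which denominator produced the printed intervals?** The exact (Clopper-Pearson) limits for x out of n at confidence 1 − a are: lower = the a/2 quantile of Beta(x, n − x + 1); upper = the 1 − a/2 quantile of Beta(x + 1, n − x).

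| Fraction | Rate | Exact interval | Printed in the plan |
|---|---|---|---|
| 6/16 | 37.5% | 90%: 17.8 to 60.9% | 17.8 to 60.9% |
| 6/15 | 40.0% | 90%: 19.1 to 64.0% | – |
| 5/15 | 33.3% | 90%: 14.2 to 57.7% | – |
| 1/16 | 6.25% | 95%: 0.2 to 30.2% | 0.2 to 30.2% |
| 1/15 | 6.7% | 95%: 0.2 to 31.9% | – |

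Both printed intervals match 16 and neither matches 15. The 16 was therefore the working denominator in two separate calculations.

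**Step 2: the 12/16 criterion.** 2 × 6/16 = 0.75, and 0.75 × 16 = 12 exactly. The one-sided 80% lower limit for 12/16 is the 0.20 quantile of Beta(12, 5) = 61.55% (printed as 61.5%). It uses only Part 2 numbers, so the Part 1 count cannot move it.

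**Step 3: what if 15 were right?** The documents give no responder count out of 15, so these fractions are assumptions.

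- 6/15: twice 40.0% is 80%, or 12.8 of 16, so 13/16 in whole participants. 12/16 is 0.75/0.40 = 1.875 times the benchmark.
- 5/15: twice 33.3% is 66.7%, or 10.7 of 16, so 11/16. 12/16 is 0.75/0.333 = 2.25 times the benchmark.

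The exact binomial probability of at least 12 responses in 16 by chance is 0.26% at a true 37.5%, 0.49% at 40.0% and 0.08% at 33.3%. The 61.5% limit exceeds all three rates.

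**Step 4: DLT boundary.** The upper line is [ln((1 − 0.20)/0.05) + n ln(0.95/0.70)] / [ln(0.30/0.05) + ln(0.95/0.70)]. It gives 1.61 at n = 2, 1.90 at 4, 2.05 at 5, 2.92 at 11, 3.07 at 12 and 3.94 at 18. Rounded up, that is 2 DLTs for n = 2–4, 3 for 5–11 and 4 for 12–18, as in Table 21. The Part 1 count does not enter.

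**Step 5: accrual.** 16/(1 − 0.10) = 17.8, rounded up to 18, as printed. The Part 1 count does not enter here either.

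**The case for a change.** The strongest case for acting is that the documents cannot prove that 15 is the slip. Only the Part 1 data can, and a benchmark corrected after Part 2 results are known could look driven by those results. One comparison would also be sensitive: the 61.5% limit lies just above the Part 1 upper limit of 60.9%, but would fall below the 64.0% that 6/15 gives.

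The first part stands as far as it goes. The mismatch is genuine, and an earlier data cut cannot be excluded. But the evidence points one way: two fractions with matching exact intervals, and a threshold that is exactly twice the rate, all use 16. The 15 supports only the remark about similar sample sizes and the contrast with six on Arm G, both of which hold equally for 16. The choice of Arm E also has the separate support that Arm G was not feasible.

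The interval comparison is not one that the plan makes. Section 9.5.2 sets a fixed criterion of 12/16, and the reference to doubling describes it.

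The implicit details are largely settled by context. Section 9.4 names Arm E, section 9.6.2 uses the same denominator for it, and section 9.5.2 opens with the 37.5% rate before concluding that the Part 2 rate is likely higher. Whether 16 means treated, eligible or evaluable is a fair question, but it does not explain 15 against 16. An analyst would settle it by tabulating each set with the section 9.7.2 definition.

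**Conclusion.** A clerical inconsistency that calls for no change to the plan. The counts differ by one participant, and the isolated value is the 15 in section 9.0. It enters no calculation, threshold or stopping rule. The 12/16 criterion, the 61.5% limit, the DLT boundary and the target of 16 eligible (18 in total) all reproduce as printed.

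This rests on 16 being the correct Arm E count, which the matching intervals make likely but do not prove. The ordinary tabulation of Part 1 results by arm under section 9.7.3 would show the true number. If it turned out to be 15, the response rate, both Part 1 intervals and the description of 12/16 as a doubling would need restating (1.875 times the benchmark for 6/15, 2.25 times for 5/15). A result of 12/16 would still be very unlikely at either rate, at 0.49% and 0.08%.

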#### 5.4.2 Regimen

Part 1: Each vaccine will be administered at a different site, rotating among available extremities when possible.

Part 2: The same skin location will be used for all vaccines. If the vaccine site has severe inflammation or ulceration after multiple vaccines, the next vaccine may be placed adjacent to the original site.

Chronic inflammatory reactions at the vaccine sites are expected to occur in all participants who receive Montanide ISA-51. Induration may persist for days to months, but is not expected to require additional therapy. Sterile abscesses may occur in some participants. These are not a basis for discontinuation of the vaccines. However, if the inflammatory reactions develop significant ulceration of the skin (> 2 cm), then this would be considered a dose-limiting toxicity and the patient would be taken off the study.

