## 5.4.3 Vaccination doses:

# Part 1:

For each vaccine, 300 mcg of each of the long peptides in LPV7 and 200 mcg of the tetanus helper peptide will be administered, plus 1 ml IFA or the dose of TLR agonists as specified in Table 1A and section 5.2.1.

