#### Part 2:

For each vaccine, 300 mcg of each of the long peptides in LPV7 will be administered, plus 1 ml IFA and the dose of TLR agonists as specified in Table 1B and Section 5.2.1.

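### Section 9.5.2 credits 12 or more responses out of 16 to single-site injection, but Arm E2 also drops the tetanus peptide and is a non-randomised, single-institution cohort, so the result speaks to the regimen as a whole

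*Combined protocol and SAP*

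**What the plan says.** Section 9.5.2 takes its reference from Part 1: "Immune response was observed in 6/16", or 37.5% with a 90% confidence interval of 17.8 to 60.9%. Part 2 aims for 16 eligible participants. If at least 12 respond, described as a doubling of the rate, the lower limit of a one-sided 80% interval would be 61.5%, "which we would conclude supports that the immune response rate is likely to be higher for single site injections". If fewer respond, further studies are called for to "better understand the impact of site rotation with the use of the tetanus helper peptide".

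Two features of the vaccine change between the parts:
- **Site.** Part 1 rotated the injection site. For Part 2, section 5.4.2 says "The same skin location will be used for all vaccines".
- **Content.** In Part 1, section 5.4.3 says "300 mcg of each of the long peptides in LPV7 and 200 mcg of the tetanus helper peptide will be administered". In Part 2 it says "300 mcg of each of the long peptides in LPV7 will be administered, plus 1 ml IFA", with no tetanus peptide.

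The Précis and section 3.1 give three reasons for the omission: the peptide is no longer available, the LPV7 peptides were found in Part 1 to induce helper responses themselves (unpublished), and earlier data with another peptide vaccine showed no significant gain from adding it. Section 4.4.2 says that Part 2 is not randomised, and the Précis places it at one of the two institutions.

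The Arm E count is given in two ways. Section 9.0 says "the total enrollment on Arm E is larger (15 vs 6" for Arm G). Section 9.6.2 reports that 1/16 "participants treated on Arm E experienced a DLT".

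**The concern.** When two components change together and there is no concurrent control, a higher E2 rate shows at most that E2 did better than the earlier cohort. It does not show which change was responsible, or whether the cohorts differed in other ways. The success sentence nevertheless names one component only. The failure sentence names both, so the tetanus peptide qualifies a disappointing result but not a favourable one.

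What is at stake is the claim that a 16-participant pilot may make, and how its result is used. Section 1.1 says that Part 2 will inform both the decision to run a definitive randomised trial of site and the powering of that trial. If the E2 minus E difference were carried into that calculation as the effect of site, it would carry the wrong label.

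**Working it through.** **Inputs.** Reference 6/16, n = 16, threshold 12, and a one-sided 80% lower limit of 61.5% (all section 9.5.2). The Arm E counts of 15 and 16 are from sections 9.0 and 9.6.2. The documents give no effect size for omitting the tetanus peptide, so the shifts below are assumptions shown as a range.

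**1. The plan's own figures reproduce.** The exact (Clopper-Pearson) lower limit for x of n at one-sided level 1 − a is the a-quantile of Beta(x, n − x + 1).
- 12/16, a = 0.20: Beta(12, 5) gives 0.6155, the stated 61.5%. For comparison, 11/16 gives 55.1%.
- 6/16, two-sided 90%: 0.178 to 0.609, the stated 17.8 to 60.9%.

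**2. Chance of meeting the rule with no site effect.** P(X ≥ 12) = Σ from k = 12 to 16 of C(16, k) p^k (1 − p)^(16 − k), with p = 0.375 + d. Here d is the shift due to omission, or to any other non-site difference.

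| d (assumed) | p | P(at least 12/16) |
|---|---|---|
| −10 points | 0.275 | 0.01% |
| 0 (neutral) | 0.375 | 0.3% |
| +10 points | 0.475 | 2.4% |
| +20 points | 0.575 | 12.1% |

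For a 20% chance of success from a non-site cause alone, p must be about 0.615, a shift of 0.615 − 0.375 = 24 points. For a 50% chance, p must be about 0.714, a shift of about 34 points.

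The table takes 37.5% as the true base rate. That rate is itself estimated from 16 people: at the top of its stated interval, 60.9%, the rule would be met 18.6% of the time with no change at all.

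**3. What differs between E and E2.**

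| Feature | Arm E (Part 1) | Arm E2 (Part 2) | In success sentence? |
|---|---|---|---|
| Injection site | rotating | same | yes |
| Tetanus peptide | given | omitted | no |
| Timing | completed | later | no |
| Institutions | two | one | no |
| Allocation | within the Part 1 scheme | all to E2, no randomisation | no |

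Step 2 bears on whether E2 differs from the Part 1 rate. It cannot divide a difference among the rows of this table.

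**4. The Arm E count.** Section 9.5.2 attributes 6/16 to Part 1 without naming the arm; section 9.6.2 has 16 treated on Arm E; section 9.0 has 15 enrolled. If 15 were right, the numerator would also need checking. The exact 90% upper limit is 64.0% for 6/15 and 57.7% for 5/15, and the documents support neither as the corrected value.

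**The case against.** The strongest reply is that the plan already treats the omission as neutral and gives reasons in the Précis and section 3.1. If omission is neutral or harmful, it cannot produce a false site claim. That would require removing a helper peptide to raise the CD8 response, and nothing in the documents suggests that it would. The success sentence is hedged, Part 2 is described as a pilot giving preliminary data, and section 1.1 leaves the site question to a randomised trial.

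Most of this stands, and it is why the point is limited to wording. It does not dispose of the point. An unpublished finding and a non-significant result with a different vaccine do not establish no effect. Neither reason addresses the change of cohort and institution. The sentence that licenses the conclusion mentions none of this.

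Four stronger readings are tempting, and the documents do not support them:
- *The tetanus change was overlooked.* It is justified in two places and named in the failure branch. What is missing is the link to the success branch.
- *The threshold is lax.* At a true 37.5% it is met 0.3% of the time.
- *Omission could hide a real site effect, so the rule is unsound.* Omission could lower the response, but with fewer than 12 responses the plan draws no negative conclusion about site and asks for more study.
- *The 61.5% limit fails its comparator.* The plan never says that 61.5% is to be compared with 60.9%; its stated rationale is a doubling of the rate. The limit falls short of 64.0% (6/15) but clears 57.7% (5/15), so any such failure rests on an inferred comparator and an assumed count.

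**Conclusion.** The point holds as a minor to moderate correction of what may be concluded, not of the threshold or the sample size. At least 12/16 would support a higher response rate for the E2 regimen than in historical Arm E. It would not by itself support a site effect.

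The practical risk of a false site claim is small: 0.3% if omission is neutral, and 2.4% or 12.1% if it adds an assumed 10 or 20 points. These figures assume a true base rate of 37.5%, comparable cohorts and no site effect.

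For powering a later trial, the E2 rate is a fair input for a same-site arm without the tetanus peptide. The E2 minus E difference is not a pure site effect, because no cohort supplies the rotating-site rate without that peptide.

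The conflict over the Arm E count is real, but it is a separate matter of reconciliation and adds nothing to the attribution argument.

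**What to change.** 1. In section 9.5.2, reword the success branch: at least 12/16 supports a higher immune response rate for the E2 regimen as a whole (same site, no tetanus peptide) than in historical Arm E.
2. Add one sentence: a site-only reading assumes both that omitting the tetanus peptide does not raise the response and that the cohorts are comparable although non-concurrent and drawn from one institution versus two; that reading is left to the randomised trial foreseen in section 1.1.
3. State that the E2 minus E difference will not be used as a pure site effect when powering that trial.
4. Separately, reconcile the Arm E count across sections 9.0, 9.5.2 and 9.6.2, name the arm behind 6/16, and restate the rate and its interval if the count changes.

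The cost is a few sentences and a check of one count from the completed Part 1. The permitted claim becomes weaker. Sample size, threshold, data collection and participant procedures do not change.
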